7. SAFETY ASSESSMENTS

We do not foresee any risks to subjects in participating in either the MBSR or HLC interventions. MBSR is fundamentally an educational intervention and has been shown to be an effective adjunctive intervention in reducing medical symptoms for a broad range of stress-related disorders and chronic diseases, reducing psychological distress including anxiety and depression, and improving quality of life. The potential risks to participants in MSBR include psychological or social stress that might result from discussions in class. We believe that this is a minimal risk and the instructors of these classes have received excellent training on how to help individuals presenting such issues. The HLC is a series of lectures and discussions similar to those offered through the UMMHC's Community Programs office and are fundamentally educational in nature. The potential risks to participants in the HLC would be limited to psychological or social stress that may result from discussions in class. We believe this is a minimal risk and will ensure all lecturers are prepared to address

these issues should they arise.

The psychosocial assessments are standardized and widely-used paper and pencil surveys. The spirometry assessment procedures are ones asthma patients will be already familiar with from their standard medical management and do not involve risk to the patient. Likewise, the Breath Perception Discrimination Test (BPDT) that measures ability to detect small changes in resistive load will be done in the Pulmonary Diagnostic Laboratory at each site following the spirometry and does not pose any risk to participants.

A clinically significant change in spirometry reading is defined as a decrease of 15% or more from baseline to any follow-up assessment point. To monitor for untoward respiratory symptoms, the study pulmonologist, [name], will review all participants' de-identified spirometry readings at each assessment point and compare them with their prior readings and use his clinical judgment as to whether there is any cause for concern. Should this occur, this finding will be reported to both the participating patient and the patient's pulmonologist so that they are aware of the decrease and can formulate an appropriate treatment plan.

7.1. Specification of Safety Parameters

N/A

7.2. Methods and Timing for Assessing, Recording, and Analyzing Safety Parameters

N/A

7.3. Adverse Events and Serious Adverse Events

An **adverse event** (AE) is any untoward medical occurrence in a subject during participation in the clinical study or with use of the experimental intervention being studied. The AE either occurs during the study, having been absent at baseline, or if present at baseline, appears to worsen. An adverse finding can include a sign, symptom, abnormal assessment (e.g., laboratory test value), or any combination of these.

A **serious adverse event** (SAE) is defined as any AE that results in one or more of the following outcomes: death, a life-threatening event, inpatient hospitalization or prolongation of existing hospitalization, a persistent or significant disability/incapacity, or an important medical event based upon appropriate medical judgment. Given the nature of the study interventions, a congenital anomaly or birth defect is a highly unlikely event and this outcome has been excluded for the present trial.

7.4 Reporting Procedures

We anticipate very minimal risk to subjects due to their participation in this study. Although our study poses minimal risk to subjects and no adverse events are expected due to the nature of the study, we will follow the adverse event procedure of the University of Massachusetts Medical School.

The University of Massachusetts Medical School/UMMC will be the coordinating institution and receive reporting of all AEs from both study sites. The current policy for reporting unanticipated problems and adverse events for the protection of human subjects in research is as follows: Any harm experienced by a subject which, in the opinion of the investigator is **unexpected** and **probably related** to the research procedures, must be reported to the IRB within 5 business days using the appropriate reporting form. A harm is "**unexpected**" when its specificity or severity are inconsistent with risk information previously reviewed and approved by the IRB in terms of nature, severity, frequency, and characteristics of the study population. A harm is "**probably related**" to the research procedures if in the opinion of the investigator, the research procedures more likely than not caused the harm. If the study is part of a multicenter trial as is this one, any AE reports received from the other sites should be sent to the UMMS IRB within 5 days of when they are received. Adverse events that do not meet the requirements of prompt reporting should be provided at the time continuing review is submitted. The continuing review form in the UMMS eIRB will request this information.

To assess for the occurrence of adverse events, at each assessment point participants will be asked the question: "Have there been any changes in your health since we last saw you?" We also will collect AEs that are volunteered spontaneously during interactions with participants. Any Miriam AEs will be faxed within 24 hours to the UMMS PIs. In addition, we will consider a clinically significant change in spirometry reading, defined as a decrease of 15% or more from baseline to any follow-up assessment point, as an AE. Should this occur, this finding will be reported to the patient's pulmonologist/physician so that they are aware of the decrease and allow the physician to decide if/how to follow up with the patient as appropriate.

7.5 Follow-up for Adverse Events

Should a clinically significant change in spirometry reading (defined as a decrease of 15% or more from

baseline to any follow-up assessment point) occur, this finding will be reported to both the participating patient and the patient's pulmonologist/physician so that they are aware of the decrease and can formulate an appropriate treatment plan.

All SAEs will be followed to resolution (the subject's health has returned to his/her baseline status or all variables have returned to normal); or followed until stabilization of the event has occurred (the investigators do not expect any further improvements or worsening of the event; or the event is otherwise explained regardless of whether the subject is still participating in the study. Some events do not end, such as metastasis; however, once these events are determined by the PIs to be stable or chronic, the PIs may consider the event to be resolved or resolved with sequelae.

The Human Subjects Committee (HSC) at UMMS is a fully authorized Institutional Review Board (IRB) that provides oversight to research conducted at the medical school. It functions in compliance with the congressional statutes governing human research detailed in the University of Massachusetts Medical School "Assurance of Compliance with Health and Human Services (HHS) Regulations for Protection of Human Research Subjects". This committee will be providing oversight to the current study.

8. INTERVENTION DISCONTINUATION

MBSR has been used clinically for over two decades without any reported significant untoward effects. HLC is an educational program. We do not anticipate that any significant proportion of individuals will require discontinuation of either intervention. However, participants will be monitored at each intervention session. If individuals report moderate to severe discomfort from participation in MBSR or HLC, the participant will be extensively debriefed to ascertain the nature of the discomfort. They will be offered the choice of continuing or withdrawing from the study.

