Perceived Stress	Perceived Stress Scale (PSS), ⁹⁴ a well-validated 10-item scale based upon the transactional model, ⁶⁹ measures degree to which situations in one's life over the past month are appraised as unpredictable, uncontrollable and overwhelming. A higher score indicates a greater degree of perceived stress, and lower scores are associated with better coping resources. ⁹⁵ Higher PSS scores have been associated with failure to make health-promoting behavior changes. ^{96, 97} Participation in MBSR has been associated with significant declines in PSS scores. ⁹⁸	■	■	■	■
Moderating/Process Variables					
Sociodemographic Variables	Age, gender, race/ethnicity, years with asthma diagnosis, number of years taking asthma medication, body mass index, education level, marital status, employment status.	■			
Medical and Psychiatric History	Focused medical history, comorbid medical conditions, medications, smoking status, physician and ER visits, hospitalizations, and focused psychiatric history	■	■	■	■
Adherence to MBSR and HLC Requirements	Number of MBSR and HLC classes attended will be documented by instructors delivering the MBSR and HLC classes. Completion of homework during intervention will be assessed by participants recording number of minutes of home practice they do each day using homework logs. ⁶² During follow up, MBSR participants will estimate the usual minutes of mindfulness practice they have been doing each week in the interval since their last assessment. Participants who attended four or fewer intervention classes will be asked their reasons for non-attendance		■	■	■
MBSR and HLC Fidelity	MBSR instructors at both sites will participate in the ongoing weekly supervision meetings conducted with UMass Center for Mindfulness MBSR instructors to ensure fidelity to MBSR protocol. HLC instructors at both UMMS and Miriam will have weekly supervisory meetings with [name] in which curriculum delivery is reviewed and potential threats to fidelity are discussed.				
Days of Work/School Missed	Self-report of number of days of work or school missed because of asthma in the 6 months prior to each assessment.	■	■	■	■
Triggers/Seasonal Variability	Self-report from list of 11 common asthma triggers (e.g. aspirin, cold air, infections etc.), and the months of the year their asthma is worse	■	■	■	■

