Confounding Effects	A Confounding Effects Inventory (CEI) developed in our pilot study documents common confounding effects experienced in the past 6 months that could impact asthma control. These include environmental confounders in the home (moved, changes in active or passive smoking, pets), workplace, and social environments; medical problems (sinus infections, upper and lower respiratory tract infections, other infections, gastroesophageal reflux disease, surgery, and new diagnosis or change in status of other cardiovascular or respiratory conditions); changes in asthma and other medications; and changes in health insurance coverage.	■	■	■	■
CAM Use for Asthma/Concomitant Interventions	Self-report of CAM treatments for asthma (e.g. acupuncture, homeopathy, herbal medicine, prayer, supplements, dietary restrictions) in the 6 months prior to each assessment.	■	■	■	■

6.2.1. Screening Evaluation: Upon obtaining verbal consent the RA will complete the eligibility screen which will include questions related to the eligibility criteria using a script and screening form to standardize this phase of enrollment. Criteria for eligibility (inclusion and exclusion criteria) are listed in sections 4.1 and 4.2. A 6-week range will be allowed prior to study entry during which all screening evaluations to determine eligibility will be completed.

6.2.2. Participant Consent, Study Enrolment, Baseline Assessment and Randomization: Eligible persons will attend an orientation session on the day of their clinic visit or, if the RA was not able to be at the clinic on the day of their visit, at the study offices at that site during which the site RA will explain in full detail the study goals and procedures so as to familiarize the patient with what to expect, and what is expected from their participation in both the interventions and the assessments. Subjects will be informed about all of the risks

described above and all aspects of the study, and emphasize that their participation is voluntary and that they may withdraw at any time by contacting the RA and/or the contact PI. Contact information for the RA and the PI, as well as the IRB (for complaints) is contained in the consent form.

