Retention of Participants: We expect to retain 85% of participants at 18-months. Contact information will be collected from the participant at enrollment. Tracking procedures will be established and implemented for those not completing a scheduled study assessment, or who cannot be reached. Attempts to locate participants will be made by telephone calls to family, family contacts, and directory assistance. Incentive gift certificates will be provided: \$50 for completing assessments at each of the baseline and 6-month follow-ups, and \$75 at 12- and 18-month follow-up. The UMMS Project Director, [name] will oversee retention at both sites.

6.2.3. Blinding: All study staff except the Research Assistant, and Project Director Database Manager ([name]) will be blinded. Blinding the Research Assistant, Project Director, and Database Manager would be impractical given that they will be randomizing the patients to the intervention groups, or tracking the randomization process. The impact of un-blinding the Research Assistant, the Project Director and the database manager will be minimal because evaluation surveys are completed directly by participants, and they will NOT perform any data entry or statistical analysis. The pulmonary lab technicians (for outcomes measurement) will be blinded, as well as the PIs, study statistician, and all study investigators and those involved with randomization codes. These un-blinded staff will have no access to the data, no influence on the outcome assessments, and no involvement in data analysis. Staff delivering the interventions and preparing reports for the independent monitoring will not be blinded.

The study arms will be coded and referred as non-informative A vs. B, but not intervention vs. control, or a coding revealing the nature of intervention arms. The non-informative coding/naming of intervention arms will be kept until the planned main outcomes analysis is completed. Unblinded project staff are prohibited to reveal the information on the coding of study arms to anyone.

The blind will be broken in the case of a serious adverse event. In this event, Drs. [name] and [name], the study pulmonary physicians, will break the blind in order to address the SAE.

The data and safety monitoring board (DSMB) will also be blinded unless the unblinding is needed to investigate severe adverse events or other patient safety issues, required by NCAAM, IRB or law.

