In case the unblinding is necessary, the process will be formally monitored and documented. The PI's will draft a request for permission to unblind the codes to NCCAM, IRB and the DSMB. With the permission, the PI's will work with the database manager to reveal the study arm codes to the individuals authorized by the PI's, DSMB, NCCAM and DSMB. Hand signed documents will be kept by the database manager, and copied to DSMB, IRB and NCCAM. Unblinded individuals will be excluded from first round of statistical analysis of the main outcomes.

6.2.4 Follow-up Visits: As described in Section 6.1, study follow-up visits will occur 6- months, 12- months, and 18-months post-baseline. Section 6.2 describes the assessments that will occur at each of these time-points. Study assessment visits indicated in Section 6.2 will occur within a 3-week period before and after the 6-, 12-, and 18-month timeframes.

6.2.5 Completion/Final Evaluation: The final evaluation will be conducted at the 18-month post-baseline assessment and will consist of the assessments listed in Section 6.2 for this visit. We do not foresee any reason for participants' early termination from the study. However, any participants who discontinue study intervention early will be invited to complete all study evaluations.

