11.2. Informed Consent Forms

Consent will be obtained at two time points during the study: 1) at the initial phone screening, and 2) at the orientation session.

1) As in our prior studies, a HIPAA waiver authorization will be requested from our respective Institutional Review Boards prior to obtaining the list of apparently eligible patients. Interested patients will be called by the Research Assistant (RA) at each site. The RA will briefly describe the study and its requirements and it will be explained that the patient’s overall care at their hospital will in no way be affected by whether or not the patient participates in the study. The RA will then enquire if the patient is still interested. If the caller is interested the RA will explain the need to collect some information from the patient to determine whether they are eligible to participate and request verbal permission to proceed. Upon obtaining verbal consent the RA will complete the phone screen which will include questions related to eligibility. A script and screening form will be used to standardize this phase of enrollment.

If the patient is eligible, the RA will schedule an in-person consent/baseline session with that individual.

2) Eligible persons will attend a consent/baseline session at the study offices at that site during which the RA will explain the study goals and procedures. This will be designed to familiarize potential participants with the study, what to expect and what is expected of their participation, both in the interventions and research assessment aspects of the study. Individuals who wish to enroll will provide written consent using an IRB-approved and dated consent form. In addition to describing the study and the participant’s involvement in detail, the consent form also emphasizes that participation is voluntary, that consent may be withdrawn at any time, and that participants may withdraw from the study verbally or in writing by contacting the study RA and/or

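### Section 8 offers a participant distressed by the classes only continuing or leaving the study, which is inconsistent with section 6.2.5 and could create avoidable missing data

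*Combined protocol and SAP*

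**What the plan says.** Section 8 is headed as dealing with discontinuation of the intervention. It expects no significant proportion of participants to need to discontinue. For someone who reports moderate to severe discomfort from either programme it requires an extensive debrief, and then: "They will be offered the choice of continuing or withdrawing from the study". It does not refer to any other section.

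Section 6.2.5 foresees no reason for early termination from the study, but provides that "any participants who discontinue study intervention early will be invited to complete all study evaluations".

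Two other provisions in section 6.2 assume that people who stop attending stay under observation. The adherence row of the evaluation table states: "Participants who attended four or fewer intervention classes will be asked their reasons for non-attendance". The retention paragraph of 6.2.2 states: "Tracking procedures will be established and implemented for those not completing a scheduled study assessment".

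Section 11.2 uses the language of study withdrawal for leaving the trial: "participants may withdraw from the study verbally or in writing by contacting the study RA".

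Sections 9.3 and 9.6 make the primary analysis intent-to-treat, with participants analysed in the arm to which they were randomized.

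**The concern.** An intent-to-treat comparison needs outcomes from everyone randomized, whether or not they finish the classes. Stopping the intervention and leaving the study are therefore separate events. Section 6.2.5 keeps them separate; the two options stated in section 8 do not.

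The people section 8 covers are those whose reason for stopping is the class they were assigned. The classes differ between arms, so losses of this kind could differ by arm and could relate to outcome. Section 9.6 plans inverse probability weighting, and sections 9.3 and 9.6 plan multiple imputation. The outcome-dependent weighting example in 9.6 uses an outcome from the preceding time point. Anyone who left before the 6-month visit would have no follow-up outcome, so adjustment would rest on baseline data in place of scores that might have been collected.

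There is also a safety side. Section 7 names psychological or social stress from class discussion as the potential risk of both programmes. Recording the affected people as withdrawals would end their scheduled safety observation.

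**Working it through.** The point rests on wording, so the first step is to set the provisions side by side. The arithmetic only bounds the size.

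**1. The same person under each provision.** Take a participant who reports discomfort, is debriefed, and wants to stop classes but has no objection to assessments.

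- Section 8: the options are to continue or to withdraw from the study. Neither describes what this person wants.
- Section 6.2.5: the person has stopped the intervention early and is invited to all evaluations.
- Section 4.3: a person who misses a class without reporting discomfort is called to work through the barriers to attending.
- Section 5.4: attending fewer than five of the nine classes, with the homework for those classes not done, is a protocol deviation. It is not a withdrawal.
- Section 6.2: someone who attended four or fewer classes is asked why at follow-up, which presupposes that the person is still in follow-up.

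Section 8 is the only one of these that links stopping because of the class to leaving the study.

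**2. What one such person could lose.** Assessments after baseline fall at 6, 12 and 18 months. The most that can be lost per person is:

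- three ACQ scores, the primary outcome;
- three askings of the health-change question (section 7.4: "To assess for the occurrence of adverse events, at each assessment point participants will be asked the question");
- three spirometry comparisons with baseline, where a fall of 15% or more counts as an adverse event.

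Two safety routes are less exposed. Section 7.4 also collects events that participants volunteer, and section 7.5 follows serious adverse events "regardless of whether the subject is still participating in the study".

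**3. The plan's allowance for loss.** Section 9.2 gives 254 recruited and 216 analysed.

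- 216 / 0.85 = 254.1 and 254 × 0.85 = 215.9, so the stated figures reproduce.
- Allowed losses: 254 − 216 = 38, and 38 / 254 = 15.0%.
- One person is 1 of those 38, and 1 / (254 / 2) = 1 / 127 = 0.8% of an arm. This is true of any dropout for any reason, so it does not measure this issue.

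**4. Power if losses exceeded the allowance.** Inputs from section 9.2: difference 0.25, SD 0.66, within-patient correlation 0.45, physician correlation 0.05, 9 patients per physician, 5% level (taken as two-sided).

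- Variance factor for the mean of three follow-ups: f = (1 + 2 × 0.45) / 3 = 0.633. With baseline adjustment: f = 0.633 − 0.45² = 0.431.
- Physician design effect: 1 + 8 × 0.05 = 1.4.
- At 108 per arm, SE = 0.66 × √(0.633 × 1.4 × 2 / 108) = 0.0846.
- Power = Φ(0.25 / 0.0846 − 1.96) = 84.0%. With f = 0.431 it is 94.8%. Both agree with the plan's claim of at least 80%.

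The documents give no rate of discomfort withdrawals, so the extra loss beyond 15% is an assumption:

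| Extra loss | Patients left | Power, mean of follow-ups | Power, with baseline adjustment |
|---|---|---|---|
| 0% | 216 | 84.0% | 94.8% |
| 1% | 213 | 83.6% | 94.5% |
| 2% | 211 | 83.2% | 94.3% |
| 5% | 203 | 81.8% | 93.5% |
| 10% | 190 | 79.3% | 92.0% |

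An extra 1% to 2% costs less than one percentage point. Power is not the issue, and these figures do not measure bias.

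**The case against.** The strongest reply is that section 6.2.5 already settles the matter. It covers every participant who stops the intervention early, which includes those who stop after a section 8 debrief. Section 8 is silent on the invitation and does not forbid it, so the two can be applied together. Its heading and opening sentences concern the intervention, which makes the reference to the study plausibly loose wording. Attendance records, the deviation rule and the question to low attenders already separate stopping classes from leaving.

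Most of this stands. The intended policy is clear, and the inconsistency causes harm only where section 8 is applied alone. It remains a defect because section 8 is where staff would look when someone is distressed. It states two options, does not point to 6.2.5, and uses the same language that 11.2 uses for leaving the trial.

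A reader might infer four stronger things that the documents do not support:

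- **That participants are not told they may stay in follow-up.** The consent form is a separate document and the debrief content is not given. Only what section 8 says can be judged.
- **That the general withdrawal statement in 6.2.2 reinforces section 8.** It says that "their participation is voluntary and that they may withdraw at any time by contacting the RA", but names no object of withdrawal and comes just after a description of both interventions and assessments.
- **That all such participants would have only a baseline ACQ.** The wait from baseline to randomization is not stated, so this cannot be established.
- **That section 8 will lose data or bias the ACQ comparison.** No discomfort rate, split by arm or outcome difference is given.

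**Conclusion.** The inconsistency is real and worth correcting, but it does not threaten the trial. It could produce avoidable missing outcomes among people whose reason for stopping is the assigned class, a reason that could plausibly differ by arm. That consequence depends on staff applying section 8 without 6.2.5, and on participants who would have accepted assessments being recorded as withdrawn. The documents show neither. The size of any effect on the ACQ comparison cannot be derived from them. The protocol's own expectation of few discontinuations points to a small one.

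**What to change.** Reword the last step of section 8 to offer three choices after the debrief:

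1. continue classes;
2. stop classes and remain in the 6-, 12- and 18-month assessments under section 6.2.5;
3. at the participant's own request, withdraw from the study.

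Record stopping the intervention separately from leaving the study, with reason and date for each. The case report forms are not in the documents, so part of this may already be captured.

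The cost is one revised passage and at most one added data field. The visits are already scheduled, and neither the sample size nor the analysis changes. The downside is that choice 2 asks a distressed participant for further assessments. It must therefore stay voluntary, with choice 3 open at any time.
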